7.4.2 Reporting Serious Adverse Events

The Sponsor will collect SAEs from the time of signing of the informed consent form (ICF) until 30 days after administration of the last dose of study drug(s)/IMP(s) or until the start of a new antitumor therapy or until the date of death, whichever occurs first. Beyond this period of time, only those SAEs suspected to be related to the IMP will be collected. Nonetheless, the Sponsor will evaluate any safety information that is spontaneously reported by an Investigator beyond the time frame specified in the protocol.

All SAEs (as defined above) occurred after patient registration regardless of relationship to the study drug(s)/IMP(s) must be reported immediately, and always within 24 hours to the Pharma Mar S.A. Pharmacovigilance Department, electronically by completing the applicable e-CRF section.

SAEs occurring during the screening phase (from ICF signature to randomization), SAEs that may occur off-study, or in case the electronic system fails or is not available, will be reported within 24 hours to the Pharmacovigilance Department using the paper SAE form by fax ([contact]), e-mail ([contact]) or telephone ([contact]).

Out of office hours [Greenwich Meridian Time (GMT)], assistance on SAE reporting can be obtained by calling the Pharmacovigilance Department at [contact]. SAEs initially reported by alternative methods (not electronically), must be followed by a completed electronic SAE reporting on e-CRF from the investigational staff within one working day.

All SAEs suspected to be related to the IMP(s) must be followed until the event or its sequelae resolves or stabilizes at an acceptable level by the Investigator.

7.4.3 Reporting Pregnancy Cases Occurred within the Clinical Trial

National regulations require that clinical trial Sponsors collect information on pregnancies occurring during clinical trials, in which exposure to the IMP(s) at any time during pregnancy, via either maternal or paternal exposure, is suspected.

Therefore, pregnancy and suspected pregnancy (including a positive pregnancy test regardless of age or disease state) of a patient occurring while on study drug, or within 30 days after the administration of the last dose of the study drug(s)/IMP(s), are considered immediately reportable events. Beyond this timeframe, the investigator will report any pregnancy if there is any suspicion that the study drug(s)/IMP(s) might have an impact on the occurrence of the pregnancy.

The Investigator will report the following events immediately and always within 24 hours from first knowledge:

- Any occurrence of a pregnancy where any kind of exposure to the IMP(s) is suspected.
- Possible exposure of a pregnant woman.
- All reports of elevated/questionable or indeterminate beta human chorionic gonadotropins (β -hCGs).

Immediately after detecting a case of suspected pregnancy in a patient, the decision on her continued participation in the clinical trial will be jointly taken by the patient, the Investigator and the Sponsor, with the patient's best interest in mind. A decision to continue the pregnancy will require immediate withdrawal from the trial.

Any pregnancy, suspected pregnancy, or positive pregnancy test must be reported to Pharma Mar S.A. Pharmacovigilance immediately using the Pregnancy Report form.

The Investigator will follow the pregnancy until its outcome, and must notify Pharma Mar S.A. Pharmacovigilance the outcome of the pregnancy within 24 hours of first knowledge as a follow-up to the initial report.

For any event during the pregnancy which meets a seriousness criterion (including fetal or neonatal death or congenital anomaly) the Investigator will also follow the procedures for reporting SAEs (complete and send the SAE form to Pharma Mar S.A. Pharmacovigilance within 24 hours of the Investigator's knowledge of the event).

All neonatal deaths that occur within 30 days of birth should be reported, without regard to causality, as SAEs. In addition, any infant death at any time thereafter that the Investigator suspects is related to the exposure to the study drug(s)/IMP(s) should also be reported to Pharma Mar S.A. Pharmacovigilance by facsimile within 24 hours of the Investigators' knowledge of the event.

7.5 ADVERSE EVENTS MONITORING

Safety review will be performed at Pharma Mar S.A. once SAE forms have been received and the CRFs electronically completed by the Investigator.

At every monitoring visit performed by the designed clinical research monitor in charge of the study, the consistency between the CRF/SAE data reported to the Pharmacovigilance Department and the patient's source data will be reviewed. When a discrepancy is found during the review, data will be amended/updated in the CRF and

the SAE form/information reported to the Pharmacovigilance department (when applicable), according to source data.

SAEs will be continuously collected, assessed and reported throughout all the study as per the applicable legislation by the Pharma Mar S.A. Pharmacovigilance Department. Periodic safety reviews of SAE reports including events of special interest (e.g., neutropenia and thrombocytopenia) are to be conducted and documented by the Pharmacovigilance Department.

Non-serious AEs will be verified during monitoring visits by the clinical trial monitor, who will discuss them with the Investigators, if applicable. AEs will be assessed by the Investigators and by the study team at Pharma Mar S.A. The personnel in charge of this process are defined in the section “*Study Contacts*” of this protocol. Pharma Mar S.A. Pharmacovigilance Department will review the safety data of this trial on an ongoing basis. Periodic safety review of safety data from the clinical database, i.e. AEs and laboratory data, will be performed along the study by the Pharma Mar S.A. Pharmacovigilance, Clinical Oncology and Data Management departments.

7.6 PATIENT-REPORTED OUTCOMES

To measure the quality of life of patients, EORTC QLQ-C30 and EORTC QLQ-OV28 questionnaires will be analyzed every eight weeks from randomization and while on treatment.

7.7 PHARMACOKINETICS

7.7.1 Blood Sampling

Sparse samples (detailed in [Table 14](#)) will be collected in all patients enrolled in the PM01183 arm (Arm A). The samples will be obtained in two cycles (in Cycle 1 and in a second cycle between Cycle 2 and 4). The selection of the second cycle with sample collection for the measurement of PM01183 will be assigned once the patient is randomized into Arm A.

Table 14. Blood samples for pharmacokinetic evaluations.

Sample No.	Sampling time	PK window
#1	Before PM01183 treatment start	1 to 5 min before treatment start
#2	5 min before PM01183 EOI	+/- 2 min
#3	1 hour after PM01183 EOI	+/- 10 min
#4	168 hours after PM01183 EOI	+/- 24 hours

EOI, end of infusion; PK, pharmacokinetics.

The infusion rate will be predetermined to ensure that the dose of PM01183 is infused in 60 min at a constant rate. In order to obtain reliable PK information, the infusion rate should not be modified once the infusion begins. If a variation in the infusion time eventually occurs, it is very important this to be reflected in the CRF. The accurate recording of actual dosing and sampling times is much more important than the strict adherence to the scheduled times

Blood samples will be obtained into a vacutainer tube by using a peripheral catheter placed in a vein of the arm opposite to the side used for drug infusion. Even the last sample must never be collected from the catheter used for drug infusion.

A total of eight samples of about 4 ml each will be collected for the determination of plasma concentrations of PM01183 on Cycle 1 and in a second cycle between Cycle 2

and 4 (about 32 ml of whole blood) at the predefined times depicted in the above table. A Laboratory Manual will be provided with details on collection and storage of PK samples. Please read it carefully before PK sampling. In short, after collection, each sample will be centrifuged and the resulting plasma layer transferred into a new tube for the determination of PM01183 concentration. The plasma-containing tubes will be stored frozen until their shipment to the Central Laboratory for PK Samples (see details in the Study Contacts). All the material for PK procedures will be provided by the Sponsor(s).

7.7.2 Analytical Procedures

Plasma samples will be analyzed to determine concentrations of PM01183 using a validated, specific, and sensitive liquid chromatography/mass spectrometry/mass spectrometry (LC-MS/MS) method by or under the supervision of the Sponsor.

7.7.3 Pharmacokinetic Parameters

Pharmacokinetic analysis will be the responsibility of the Sponsor in accordance with the current Clinical Pharmacokinetics guidelines on population pharmacokinetic analyses [59, 60]. Clearance and volume of distribution will be the primary parameters of interest for the population PK analysis. Additional PK parameters will be calculated, if deemed appropriate.

7.8 PHARMACOGENETIC EVALUATIONS

To explore factors that may help to explain individual variability in the main PK parameters, the presence or absence of germline mutations or polymorphisms that may be involved in the metabolism and/or transport of PM01183 will be analyzed in leukocyte DNA extracted from one blood sample (10 ml) obtained before PM01183 treatment in Cycle 1 in patients treated with PM01183 (Arm A). The collection and management of the polymorphisms samples are quite different than those for PK assessment (please, refer to the Laboratory Manual for details). The assessment of polymorphisms is not affected by treatment. Therefore, the Sponsor may require the collection of additional polymorphisms samples later on, if the first assessment has not been performed accurately. Only patients who voluntarily sign the IC for this pharmacogenetic sub-study will participate in the pharmacogenetic evaluation. Refusal to participate in this sub-study will not affect patient participation in the clinical study PM1183-C-004-14.

7.9 PHARMACOGENOMIC (PGx) EVALUATIONS

Provision of samples for PGx analyses will be optional and performed upon patient consent by signing the PGx IC. For those patients who consent to participate in the PGx study, available tumor tissue blocks obtained at diagnosis of the disease will be collected during his/her participation in the associated clinical trial. Samples from Arm B will be used as controls in order to differentiate between the prognostic or predictive value of any obtained finding.

The following analyses will be done in paraffin-embedded tumor tissue from consenting patients:

- Quantitation of mRNA expression of selected genes involved in DNA repair mechanisms and/or related to the mechanism of action of PM01183 or to the pathogenesis of the disease by real-time qRT-PCR.
- Quantitation of protein expression of selected genes involved in DNA repair mechanisms and/or related to the mechanism of action of PM01183 or to the pathogenesis of the disease by IHC in tumor tissue microarrays constructed.
- Analysis of polymorphisms and mutations of the above mentioned selected genes will be analyzed, if relevant, by qRT-PCR and/or DNA sequencing.

Expression levels of the different markers will be correlated with the patient's clinical outcome.

8. STATISTICAL METHODS

This phase III clinical trial is designed to determine a statistically significant difference in PFS by IRC between PM01183 and a control arm with PLD or topotecan in ovarian cancer patients with platinum-resistant disease.

The primary study endpoint (PFS by IRC) will be calculated by means of the stratified log-rank test on the intention-to-treat (ITT) population, defined as all randomized patients analyzed in the group where they were allocated.

An IDMC will oversee the conduct of the study.

8.1 SAMPLE SIZE

Patients will be randomized to receive PM01183 given as 3.2 mg/m² (experimental arm, Arm A), or either topotecan or PLD (control arm, Arm B).

The prospective assumptions are a 30% reduction in the relative risk of progression or death (HR=0.7) to be achieved with the experimental arm (PM01183), at a one-sided 2.5% significance level with at least 90% power, following exponential distributions and fulfilling the proportional hazard assumption. Median PFS with control arm is expected to be around 3.5 months. It is forecasted that an observed HR of approximately 0.8 will have enough power to reject the null hypothesis.

Approximately 420 patients with platinum resistant ovarian cancer will be necessary to stratify and randomize at a 1:1 ratio over 18 months (~23 patients/month). The required 332 PFS events are expected to occur around six months after randomization of the last patient. Therefore, the IDMC meeting after the IRC review to test PFS is expected to occur about one year after randomization of the last patient.

The IDMC will review the results of the analyses. The IRC will determine the patient's best response and assign the date of objective response or progression/censoring according to RECIST v.1.1.

A futility analysis with no claim for efficacy when 210 patients are recruited and the final analysis to reject the null hypothesis (HR=1) are planned; the significance level will be determined by the actual observed number of events, and to maintain scientific integrity spending function will be defined by O'Brien-Fleming boundaries. Following the prospective assumptions, the futility analysis will occur before one year after start of recruitment. At this moment, with the available information collected after balancing efficacy and safety, the IDMC might recommend stopping the trial.

8.2 STATISTICAL ANALYSIS

Statistical analysis will be done by the Sponsor or under the authority of the Sponsor. The study protocol contains a general description; specific details will be provided in the Statistical Analysis Plan.

Frequency tables will be prepared for categorical variables, and continuous variables will be described by means of summary tables, which will include the median, mean, standard deviation, minimum, and maximum of each variable.

8.2.1 Efficacy Analyses

Time-to-event variables (PFS, OS and DR) and their set time estimates (i.e., PFS 6/12 and OS 12/24) will be analyzed according to the Kaplan-Meier method. The stratified log-rank test on the ITT population will be primarily used to compare the time-to-event variables.

Unstratified log-rank tests will also be calculated as supportive analyses. The symmetry of tumor evaluations between the different arms will be examined. Sensitivity analyses for different PFS censoring (e.g. date of progression based on scheduled time instead of registered date) will be performed, these analyses will be detailed in the SAP.

Cox regression will be used to calculate the risk reduction (PFS, OS and DR) and to evaluate the influence of the stratification variables and other potential prognostic factors on the time-to-event efficacy endpoints. Continuous variables that would have been categorized as discrete variables will also be investigated in the continuum range, and if the adjustment is better, then the continual variable will be chosen.

Counts and percentages, with their corresponding exact 95% confidence intervals, will be calculated for the binomial endpoints (i.e., response rate). The Fisher's exact test (univariate analyses) and logistic regressions will be used to compare the response rates of the experimental arm (PM01183) and the control arm (PLD and topotecan).

Waterfall plots will be used to describe the best variation of the sum of target lesions during the treatment.

8.2.2 Safety Analyses

AEs, SAEs, deaths, laboratory evaluations, dose delays/skipped/reductions and study drug discontinuations due to AEs will be tabulated in a descriptive way. Counts and percentages will be used for categorical variables, and summary tables will be used for continuous variables. Exploratory Fisher's exact tests will be performed to compare grade 4 or grade 3/4 between treatment arms.

An interim safety analysis, performed when 40 patients are enrolled in the PM01183 arm (Arm A), will test if the addition of primary CSF prophylaxis might be necessary. With the information available at that time, a Bayesian test assuming non-informative prior distribution will be done to assess the null hypothesis of febrile neutropenia $\leq 20\%$ *versus* the alternative hypothesis of febrile neutropenia $>20\%$. If the probability associated with the alternative hypothesis is higher than 50% (e.g., 8 cases out of 40 patients), the addition of primary CSF prophylaxis would be considered necessary.

At the time of the interim safety analysis, recruitment in the control arm (Arm B, PLD and topotecan) is also expected to be 40 patients.

The IDMC may request to review other preliminary safety/efficacy parameters, but no claim of superiority will be done; therefore, no type I/II error corrections will be applied.

A safety evaluation will also be performed by the IDMC as part of the futility analysis, when a total of 210 patients are included.

8.2.3 Patient-reported Outcomes (PRO) Analyses

PRO will be analyzed to determine if efficacy and side effects are accompanied by measurable changes. The analysis will be performed on summary scores of EORTC QLQ-C30 and EORTC QLQ-OV28 questionnaires, as well as on subscales, and individual symptoms.

8.2.4 Pharmacokinetic Analyses

Sparse PK data will be listed in the population PK-report for all patients with available concentrations in the PM01183 treatment arm (Arm A). Patients will be excluded from the PK analysis if their data do not allow for accurate assessment of the PK (e.g., improper handling of PK samples; incomplete administration of the study agent; missing time or dosing information). All concentrations below the lowest quantifiable concentration or missing data will be labeled as such in the concentration data presentation. All patients and samples excluded from the analysis will be retained in the dataset, but they will be flagged out and the criteria for exclusion documented.

Population PK analysis of plasma concentration-time data of PM01183 will be performed using non-linear mixed-effects modeling. Data may be combined with those of a selection of phase I or II studies to support a relevant structural model. Available patient characteristics (demographics, laboratory variables, genotypes, etc.) will be tested as potential covariates affecting PK parameters. Details will be given in a population PK analysis plan and the results of the population PK analysis will be presented in a separate report.

8.2.5 Pharmacogenetic Analyses

The influence of known polymorphisms on main PK parameters will be assessed by Student's test or Mann-Whitney's U test as appropriate.

8.2.6 Pharmacogenomic (PGx) Analyses

Analysis of RNA/protein expression, polymorphisms and mutations will be performed blind and with clinical data compiled only after all analyses are completed. A Fisher's exact test/logistic regression for categorical variables and log rank test/Cox regression for time to event variables will be used to test whether a specific profile is associated with clinical outcome. The prognostic value of markers will be explored for objective response, PFS and OS. In each case, if applicable, a multivariate model will be developed by stepwise selection. All tests of statistical significance will be two-sided, and significance will be set at 0.05.

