PHARMACOGENOMIC EVALUATIONS	The analysis of potential predictive factors to PM01183 treatment will be analyzed on prior available paraffin-embedded tumor tissue samples from consenting patients. Samples from Arm B will be also analyzed and used as controls in order to differentiate between the prognostic or predictive value of any obtained finding. The potential predictive factors will include genes involved in DNA repair mechanisms (such as nucleotide excision repair, homologous recombination repair or mismatch repair) and other factors related to the mechanism of action of PM01183 or to the pathogenesis of the disease, and their expression will be analyzed at the mRNA or protein level by quantitative polymerase chain reaction (PCR) and immunohistochemistry, respectively; their polymorphisms and mutations might be also analyzed, if relevant.
STUDY ENDPOINTS	
PRIMARY ENDPOINT:
 
 • Progression-free survival (PFS) by IRC is defined as the time from the date of randomization to the date of documented progression per RECIST v.1.1 or death (regardless of the cause of death). If the patient receives further antitumor therapy or is lost to follow-up before PD, PFS will be censored at the date of last tumor assessment before the date of subsequent antitumor treatment. 
SECONDARY ENDPOINTS:
 
 • Progression-free survival (PFS) per RECIST v.1.1 by Investigator's Assessment (IA). • Overall survival (OS) will be calculated from the date of randomization to the date of death (death event) or last contact (in this case, survival will be censored on that date). • Landmark analyses: 
 ○ PFS at 6 and 12 months by IRC/IA will be the Kaplan-Meier estimates of the probability of being free from progression (per RECIST v.1.1) and death at these time points. ○ OS at 12 and 24 months will be the Kaplan-Meier estimates of the probability of being alive at these time points. • Best antitumor response by IRC/IA will be the best response obtained in any evaluation according to RECIST v.1.1. Irrespectively of treatment arm, radiological and clinical tumor assessment will be performed symmetrically at baseline

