Multivariate models (main effects or including interaction terms, if appropriate) will include all stratification factors and/or prognostic factors/covariates widely reported and recognized by the scientific community: treatment (PM01183 vs. control), ECOG PS (0 vs. ≥ 1 or coded as 0 vs. 1 vs. 2) prior platinum-free interval (1-3 months vs. >3 months or used as continuous variable), prior chemotherapy (1-2 vs. 3 lines or coded as 1 vs. 2 vs. 3), geographical area (USA vs. Europe vs. rest of the world), investigator's preference for the control arm (Topotecan vs. PLD), age, age at diagnosis, race (caucasian vs. other), histology type (serous/papillary vs. other), histology grade (poorly/undifferentiated vs. other), primary tumor site (ovarian vs. other), FIGO stage at diagnosis (metastatic/locally advanced [stage III] vs. other), FIGO stage at study entry (metastatic vs. locally advanced [stage III]/other), BRCA status (mutated vs. other), clinical/radiological signs of intestinal subocclusion at entry (yes vs. no), site of current disease: lung/liver (yes vs. no), liver metastases (yes vs. no), number of prior metastatic sites (≤ 2 vs. >2), body mass index (BMI), height, weight, body surface area (BSA), time from diagnosis to first infusion, prior cytoreduction (optimal vs. suboptimal vs. no surgery), prior radiotherapy (yes vs. no), platinum resistance (primary vs. secondary), clinically evidence of ascites at baseline (yes vs. no), time elapsed from last dose of last prior platinum-containing regimen to randomization, prior antiangiogenic treatment

with bevacizumab (yes vs. no), prior PARPi (yes vs. no), presence of any bulky (< 50 mm vs. \geq 50 mm) lesion at baseline, measurable disease (yes vs. no), sum of all target lesion diameters, baseline CA-125, albumin value at baseline, PFS prior line, response to last platinum therapy (yes vs. no) and baseline global QoL. In addition, continuous variables categorized as discrete variables will also be investigated in the continuum range and if the adjustment is better then the continuous variable will be selected in the model.

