All variables with a good percentage of valid cases (approximately \geq 90%) will be included in the multivariate analysis. Within the multivariate stepwise Logistic/Cox regression analysis, the chosen significance level for entering an explanatory variable into the model will be 0.05 (for all variables not in the model, the one with the smallest p-value will be entered if the p-value is less than or equal to the specified significance level). The significance level for removing an explanatory variable from the model will be 0.05 (for all variables in the model, the one with the largest p-value will be removed if the p-value exceeds the specified significance level). The parameter estimates, hazard ratios/odds ratios and p-values of the variables retained in the model will be presented.

Forest plots for PFS and OS summarizing main results, stratification and factors/covariates used in multivariate analyses will be plotted⁽²⁾.

Median follow-up (FU) time for PFS and OS will be calculated in the descriptive way, only taking into account the censored values and using the Kaplan-Meier method for reversing the censoring values as described by Parmar⁽³⁾.

Concordance between IRC and IA PFS assessments will be evaluated by means of Kaplan-Meier curves. Forest plots for response will also be performed adapting them to show relevant information (e.g. percentages will be shown instead of medians).

Sensitivity analyses for different PFS censoring will be performed. The following approaches will be calculated: 1) Date of progression based on scheduled time instead of recorded date (e.g. if progression occurs in the eleventh week and assessment would have to be done in the eighth week then the expected date is used instead of the actual date); 2) First date of progression combining IRC and IA assessments (e.g. the lowest date between IRC and IA is used); and 3) Date of progression moved to the prior tumor assessment date (e.g. if progression has not been documented in the second assessment and is documented in the third assessment then progression date is moved to the second assessment).

Proportional hazard assumption for PFS and OS will be checked by means of a Cox regression including treatment and its interaction with survival time⁽⁴⁾. In case of strong rejection of proportionality, then restricted mean survival estimates will also be calculated in addition to HR^(5,6).

Main summary of efficacy analyses

Endpoint	Population	Statistics

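### The stated pharmacogenomic analysis tests association with outcome and names no treatment-by-marker term, so it does not separate predictive from prognostic markers; the SAP's BRCA covariate also leaves unknown status unclear

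*Protocol*

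**What the plan says.** **Aim.** The protocol synopsis (pharmacogenomic evaluations) describes the target as predictive: "The analysis of potential predictive factors to PM01183 treatment will be analyzed". Protocol 7.9 says why control-arm tissue is needed: "Samples from Arm B will be used as controls in order to differentiate between the prognostic or predictive value of any obtained finding". The same purpose appears in the synopsis (evaluations and endpoints), Protocol 3.2 and SAP 4.3. Protocol 1.8 gives the ultimate goal as identifying which patients will respond to or resist PM01183, so that treatment can be tailored.

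**Method.** Protocol 8.2.6, repeated in the synopsis, names Fisher/logistic and log-rank/Cox methods that "will be used to test whether a specific profile is associated with clinical outcome". It continues: "The prognostic value of markers will be explored for objective response, PFS and OS". On model building: "In each case, if applicable, a multivariate model will be developed by stepwise selection". On error rates: "All tests of statistical significance will be two-sided, and significance will be set at 0.05". It does not mention treatment as a model term, a treatment-by-marker interaction, or a comparison of marker effects between arms. SAP 8.10 leaves the detail of these analyses to separate documents.

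**BRCA.** SAP 6.2 lists the covariate as "BRCA status (mutated vs. other"). Table 11.1.1.1 (SAP 11.1.1) tabulates four categories: UK (unknown, per the abbreviation list), BRCA1, BRCA2 and not mutated. Entry to the multivariate models is limited as follows: "All variables with a good percentage of valid cases", meaning roughly 90% or more. SAP 8.8 leaves missing values out of calculations. Neither section says whether UK counts as missing.

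**The concern.** A prognostic marker goes with outcome whatever the treatment. A predictive marker changes the size of the treatment effect. A test of marker against outcome addresses the first property. The second needs the marker effect compared between arms, which is the interaction. The sub-study collects the tissue needed for that comparison, but the stated analysis does not make it.

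At stake is how biomarker findings are read. A marker found by association alone could be taken forward for selecting patients for PM01183 when it only marks good or poor prognosis, and a predictive marker could be overlooked.

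The BRCA issue is separate and smaller. If unknown status falls into the other category, that row of the forest plot cannot be read as wild type, although DNA repair is central to the drug's proposed mechanism.

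**Working it through.** **1. The plan's own figure.** Inputs from Protocol 8.1: HR 0.70, one-sided 2.5%, 90% power, 1:1 allocation. Schoenfeld events = 4 × (1.960 + 1.282)² / (ln 0.70)² = 331 after rounding up; Freedman's formula gives 338. The stated 332 is reproduced. With 332 events power is 90.1%, and the critical HR is exp(−2 × 1.960/√332) = 0.806, matching the stated value of about 0.8. The documents give no event count or power for the biomarker analysis, so marker prevalence and consent rate below are assumptions.

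**2. What an association test detects.** Take 332 events, prevalence p = 0.50, two-sided 0.05. Power = Φ(√(D·p(1−p)) × |log HR| − 1.960), with |ln 0.70| = 0.357.
- Purely prognostic marker (HR 0.70 in both arms), pooled: √(332 × 0.25) × 0.357 = 3.25; Φ(1.29) = 90%.
- Purely predictive marker (HR 0.70 in the PM01183 arm, 1.0 in control), pooled: the average log HR is about half as large, so 3.25/2 = 1.62; Φ(−0.34) = about 37%.
- PM01183 arm alone, with half the events (166): √(166 × 0.25) × 0.357 = 2.30; Φ(0.34) = 63%. The result is the same for both marker types. With the 157 events SAP 5.2 expects in that arm: √(157 × 0.25) × 0.357 = 2.23; Φ(0.27) = 61%, again for both.

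The pooled test therefore favours the prognostic marker, and the single-arm test cannot tell the two apart.

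**3. What an interaction test can do.** Var(log ratio of HRs) = 1/(D × 0.25 × p(1−p)). At D = 332 and p = 0.50: √(332 × 0.0625) × 0.357 = 1.62; Φ(−0.34) = 37%. This equals the pooled predictive figure above because the two expressions coincide.

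| Prevalence | Ratio 0.70, 332 events | Ratio 0.50, 332 events | Ratio 0.70, 199 events |
|---|---|---|---|
| 10% | 16% | 47% | 11% |
| 20% | 26% | 71% | 17% |
| 30% | 32% | 83% | 21% |
| 50% | 37% | 88% | 24% |

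The last column assumes marker data on 60% of events. For 90% power at a ratio of 0.70, about 1,322 events (prevalence 50%) to 3,671 (prevalence 10%) would be needed.

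**4. BRCA.** Let m be mutation prevalence and u the share with unknown status, and assume carriers are equally common among patients with known and unknown status. If unknown joins other:
- Unknown share of other = u/(1 − (1−u)m).
- Undetected carriers in other: c = um/(u + (1−u)(1−m)).
- A true ratio of 0.50 is diluted to about 0.50^(1−c).

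For assumed m of 10–25% and u of 10–50%:
- The unknown share runs from 0.10/0.91 = 11% to 0.50/0.875 = 57%.
- Undetected carriers run from 0.01/0.91 = 1% to 0.125/0.875 = 14%.
- The diluted ratio is 0.50 to 0.55.

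The numerical bias is small unless the unknown share is large; the main problem is what the row means.

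**The case against.** The sub-study is labelled exploratory, Protocol 8.2 calls the protocol a general description, and SAP 8.10 sends pharmacogenomic detail elsewhere. An interaction may be specified there. Cox and logistic regression, which 8.2.6 names, can also carry one. This stands: the documents support saying that the stated analysis lacks the term, not that the biomarker programme lacks it.

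For BRCA, SAP 6.2 lists treatment among the covariates and allows interaction terms where appropriate. That permits a treatment-by-BRCA term without requiring or naming one. The UK category might also be handled as missing under SAP 8.8. Other would then mean not mutated, and the 90% rule could remove BRCA from the model. So the merging is the literal reading of the coding, not an explicit statement.

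Interaction power is low, as the table shows. That is a reason to report the estimate with its interval, not to substitute a test of a different question.

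A reader might infer that the plan would often declare a prognostic marker predictive. For instance, with HR 0.60 in both arms and 50% prevalence, a marker is significant in exactly one arm 17% of the time with 157 and 175 events, and 46% with half of them. Those figures illustrate a misreading. The plan prescribes neither arm-by-arm testing nor a rule that calls such a marker predictive, and 8.2.6 itself calls the explored quantity prognostic.

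**Conclusion.** The mismatch between aim and stated method is real. Control-arm tissue is collected to separate predictive from prognostic value, and Protocol 8.2.6 as written does not do so. At an assumed 50% prevalence with all 332 events, the stated kind of test finds a prognostic marker 90% of the time and a predictive one of the same within-arm size about 37%. The correct test is also weak, at about 37% for a ratio of 0.70 and less with partial consent or lower prevalence, so results will be exploratory either way. These figures rest on assumed prevalence, effect sizes and participation.

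For BRCA, what is established is a coding that merges unknown with not mutated if read literally, with no rule saying otherwise. It might be inferred that BRCA therefore always counts as complete and always escapes the 90% rule. The SAP does not settle that, because it does not say whether UK is missing.

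Neither point alters a primary or secondary efficacy conclusion.

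**What to change.** **Protocol 8.2.6 or the separate pharmacogenomic plan.** For each marker, fit one model to both arms with treatment, marker and treatment-by-marker terms, adjusted for the three stratification factors: Cox for PFS and OS, logistic for response. Report the marker effect in each arm, derived explicitly because the marker coefficient is the effect in whichever arm is the reference. Report the interaction estimate with its confidence interval. Base any predictive statement on the interaction, not on arm-specific p-values or stepwise selection. Label the analysis exploratory and state the expected power.

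**SAP 6.2.** Code BRCA as mutated, not mutated or unknown. Show the mutated and not-mutated rows in the forest plots, and keep unknown as its own level in the multivariate model. Do not apply the 90% rule to known status: with 10–50% unknown, known status is 50–90%, so the rule would remove BRCA almost throughout that range.

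**Cost.** A few sentences and model lines, with no new data. The price is wide intervals, which should be reported as such.
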